4.5. Trial Intervention Procedures

Participants will undergo arthroscopic soft tissue stabilization (Bankart procedure) or non-surgical treatment as described below. All participants will follow the same standardized 3-phase rehabilitation protocol.

4.5.1 Arthroscopic Stabilization (Intervention)

Patients randomized to surgical intervention will be required to undergo surgery within 3 months of enrollment. The period of 3 months between enrolment and surgery was chosen to balance practicality in a public system while also seeking to acutely repair the pathology. A focus group of Canadian surgeons was brought together in 2023 and determined this to be reasonable and clinically important. Prior to surgery, advanced imaging will be obtained: MRI, MR arthrogram or preoperative CT scan. This imaging is done as standard care for surgical planning only and will not be used to assess prognosis. For arthroscopic Bankart repair, the participant will be placed in the lateral decubitus or beach chair position. Standard diagnostic arthroscopy will be performed. The capsulolabral complex will be freed from the anterior aspect of the scapular neck. The anterior aspect of the scapular neck will be decorticated using a motorized burr. A capsuloligamentous repair will be performed with the capsule shifted from inferior to superior and repaired on the glenoid face. The number of anchors used for the repair will be left to the discretion of the surgeon (a minimum of 3 anchors recommended). Remplissage procedure will be performed at the

discretion of the operating surgeon. Participants will wear a sling for 6 weeks after surgery. Type of sling will be left to discretion of the treating surgeon. All participants will follow the standardized 3-phase rehabilitation protocol detailed below, starting 6 weeks after surgery once the sling is removed.

4.5.2 Non-surgical treatment (Control Group)

All participants will follow the standardized 3-phase rehabilitation protocol detailed below immediately after the date of consent, unless the dislocation occurred less than two weeks prior to consent, in which case the patient will wear a sling until they reach two weeks post-dislocation. This is to allow for sufficient healing and pain management prior to initiating physical therapy. Type of sling will be left to discretion of the treating surgeon.

4.6. Rehabilitation Protocol

Standardized rehabilitation protocol for both groups: This protocol was adapted from the published consensus rehabilitation guideline developed by the American Society of Shoulder and Elbow Therapists for rehabilitation following arthroscopic anterior capsulolabral repair of the shoulder²⁵. Handouts detailing the complete rehabilitation protocol will be provided to the participants to share with their physiotherapists. This protocol details certain criteria that must be met in order for participants to progress to the next phase. Progression through the phases is dependent on the successful completion of the listed criteria. The length of rehabilitation is estimated to be six weeks in both groups. Participants will be provided a document to bring to every physiotherapy visit to document progress and compliance. Physical therapists will confirm advancement criteria are met on the provided document in order for the study team to track participants' progression through the phases.

Phase I: Passive/active range of motion (ROM)

- *Stretching/PROM/AROM:* Pendulum exercises, Supine ER, Standing ER, Supine passive arm elevation, Seated-standing forward arm elevation, Behind the back internal rotation (IR).
- *Isometrics:* IR and ER at neutral, Prone row, Prone extension (do not extend past hip), Side lying ER, Rhythmic stabilization and proprioceptive exercises with therapist.

Criteria to be met to progress to phase II: 80% ROM with reference to contra-lateral shoulder, strength level 4/5 (movement against at least some resistance supplied by the examiner). ROM and strength measured in scaption.

Phase II: Strengthening

- *Stretching/PROM/AROM:* Pendulums, Standing ER / door / wall slide stretch, Hands behind the head stretch, Behind the back IR, Supine cross body stretch, Side lying IR;
- *Strengthening/Theraband:* ER, IR, Standing forward punch, Shoulder shrug, Seated row; Dynamic hug, Wall “W’s”, Side lying ER, Prone horizontal abduction “T’s”, Prone scaption “Y’s”, Prone row, Prone extension, Standing scaption “full can” exercises, Rhythmic stabilization and proprioception exercises with therapist.

Criteria to be met to progress to phase III: 100% ROM (within 5 degrees of the contra-lateral shoulder), strength level 5/5 (full strength, pain-free). ROM and strength measured in scaption.

Phase III: Advanced strengthening/functional therapy

- *Stretching/PROM/AROM:* Continue phase II exercises, ER at 90 degrees' abduction stretch;
- *Strengthening/Theraband:* Continue phase II exercises, ER at 90°, IR at 90°, Standing 'T's, Diagonal up, Diagonal down.
- *Strengthening/Dynamic:* Continue phase II exercises, Prone ER at 90 degrees' abduction, Biceps curls, resisted forearm supination/pronation, resisted wrist flexion/extension, proprioceptive neuromuscular facilitation (PNF) manual resistance with therapist, Push up progression

PT discharge criteria: no apprehension, SANE score >90%²⁶.

4.7. Assurance of Standardization of the Procedures

Differential expertise bias will be limited by ensuring that all participating surgeons will be fellowship trained in shoulder surgery and would have performed a sufficient number of cases to limit the potential for expertise bias. Based on the available literature, a minimum of 50 cases of arthroscopic Bankart repair would be required for surgeons to meet our participation requirements²⁷.

4.8. Primary Outcome

The success of the pilot study will be based upon the following *a priori* thresholds:

1. 50 patients recruited within 10 months;
2. 42 of 50 participants (85%) achieving complete follow-up at two years;
3. 85% of patients allocated to surgical intervention receiving surgery within 3 months of enrollment;
4. Less than 5 crossovers* between both groups.

***Note:** Crossovers are defined as either: 1) participants randomized to non-operative management (control group) who choose to undergo surgery in the absence of any feelings of recurrent instability or re-dislocation; or 2) participants randomized to surgical intervention who opt out of surgery prior to surgical intervention and choose to undergo primary non-operative management.

We will confirm feasibility with a “traffic light” approach to determine if the definitive trial will be feasible, require modifications or will not be feasible.

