4.12. Participant Retention

Once a patient is enrolled in the trial, the clinical site will make every reasonable effort to follow the participant for the entire duration of the study period. The expected follow-up rate for this study is greater than 90% based on similar fracture trials performed by the study investigators^{33–35}. Based on this experience, we will implement similar procedures to maintain participant retention which include:

1. Individuals will be excluded if they are likely to present problems with follow-up (refer to exclusion criteria).
2. At the time of consent, each participant will provide the name and address of their primary care physician, and the name, address and phone number of one person at different addresses with whom the participant does not live with who are likely to be aware of the participant's whereabouts as well as their own address and phone number. This information, however, will not be stored in the EDC software and will be only collected on the paper CRFs, for internal use only. The research coordinator will confirm that these numbers are accurate prior to the participant's discharge from hospital.
3. The study coordinator will remind participants of upcoming clinic visits.
4. The study coordinator will contact participants no less than once every three months to maintain contact and obtain information about any planned change in residence.

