5.0. STATISTICAL PLAN

5.1. Sample Size Determination

Pilot Study: The feasibility objectives in our pilot study do not lend themselves to traditional power calculations. Sample size is based on the precision around the estimate of compliance of 90%. A sample size of 42 patients will yield a 95% CI of 78 to 96% which we feel is adequate precision. If we account for 15% drop-out / loss to follow-up we require a total of 50 patients. Therefore, we propose a sample size of at least 50 participants (25 participants per treatment arm). We have used similar pilot sample sizes to demonstrate feasibility in our previous multi-centre trials^{33–36}. We will also aim to recruit an additional 50 participants in the non-randomized cohort.

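### The follow-up success criterion gives a count and a percentage that disagree: 42 of 50 is 84%, not 85%, so exactly 42 completers meets one and misses the other

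*Protocol*

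**What the plan says.** Protocol section 4.8 (Primary Outcome) introduces four feasibility thresholds with "The success of the pilot study will be based upon the following". The second reads "42 of 50 participants (85%) achieving complete follow-up at two years", so one criterion carries both a count and a percentage. The third reads "85% of patients allocated to surgical intervention receiving surgery within 3 months of enrollment" and carries a percentage only.

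Section 5.1 (Sample Size Determination) shows where 42 and 50 also occur. It says "A sample size of 42 patients will yield a 95% CI of 78 to 96% which we feel is adequate precision", then "If we account for 15% drop-out / loss to follow-up we require a total of 50 patients", and concludes "we propose a sample size of at least 50 participants (25 participants per treatment arm".

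Section 4.12 (Participant Retention) gives the planning expectation: "The expected follow-up rate for this study is greater than 90" per cent. Sections 4.8 and 5.2 add that feasibility will be judged by a traffic-light approach. Section 5.2 has the components reported as proportions with 95% confidence intervals. The protocol states no cut-offs for the colours.

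**The concern.** A success threshold fixed in advance should give one answer for every possible result. Here the count and the percentage are two different rules. By the count, 42 completers is enough. By the percentage it is not, because 84.0% does not round to 85%. Nothing else in the protocol says which of the two governs.

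At stake is one of the four criteria that make up the primary outcome. If the trial ended with 42 completers, someone would have to choose the reading once the result was known, which is what an a priori threshold is meant to prevent. The planned size is a minimum rather than a fixed number, so the two rules also separate further if more than 50 are randomised.

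**Working it through.** **Inputs.** Threshold of 42 of 50, labelled 85% (section 4.8). Precision sample of 42, assumed proportion 90%, loss allowance 15%, total at least 50 (section 5.1). Expected follow-up above 90% (section 4.12). True retention of 80% and 85% are assumptions, added to show the range.

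**Step 1: reproduce the sample size.**
- Inflation for loss: 42 / (1 − 0.15) = 49.4, rounded up to 50. This agrees with section 5.1.
- Interval: the Wilson 95% interval for 38/42 is 77.9% to 96.2%, which agrees with the stated 78 to 96%.

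**Step 2: check the threshold.**
- 42 / 50 = 84.0%. The stated 85% is not reproduced.
- 0.85 × 50 = 42.5, so at least 43 completers are needed.
- 43 / 50 = 86.0%.

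**Step 3: likely origin (an inference).** 42 / 49.4 = 85%, but 42 / 50 = 84%. The 42 and the 85% were probably carried over from section 5.1 without allowing for the rounding of 49.4 up to 50.

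**Step 4: which results are affected at N = 50.**
- 41 or fewer: both readings fail.
- Exactly 42: passes by count, fails by percentage.
- 43 or more: both readings pass.

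**Step 5: how much it matters.** With X the number of completers, X ~ Binomial(50, p):

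| True retention p | P(X ≥ 42) | P(X ≥ 43) | P(X = 42) |
|---|---|---|---|
| 0.90 | 94.2% | 87.8% | 6.4% |
| 0.85 | 66.8% | 51.9% | 14.9% |
| 0.80 | 30.7% | 19.0% | 11.7% |

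**Step 6: more than 50 randomised.** With 55, taken only as an illustration, 42 / 55 = 76.4%, while 0.85 × 55 = 46.75 requires 47 completers. The gap between the two rules grows from one patient to five.

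**Step 7: the surgery criterion.** With 25 in the surgical arm, 0.85 × 25 = 21.25. So 22/25 (88%) passes and 21/25 (84%) fails. There is one rule and one answer.

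**The case against.** The strongest reply is that this is a rounding slip of half a patient in a descriptive pilot. Only one result at N = 50 is ambiguous, and at 90% retention, the lower edge of what the protocol expects, it has a probability of 6.4%. The decision is also not a plain pass or fail. Under the traffic-light approach, 42 completers would most likely raise a question between feasible and feasible with modifications. The estimates hardly differ: the Wilson 95% interval is about 71 to 92% for 42/50 and 74 to 93% for 43/50. The colour cut-offs may stand in an analysis plan that is not shown.

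All of this limits the size of the point, and that much stands. It does not remove the contradiction. Section 4.8 itself states the threshold, and the mention of traffic lights does not say whether the count or the percentage defines it.

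A reader might infer three stronger things that the protocol does not support:
- **That the surgery-timing criterion is defective too, because 85% of 25 is not a whole number.** A percentage cut-off need not fall on an integer, and there is no second figure for it to contradict. It also copes better than a fixed count if the surgical arm is not exactly 25, which is possible with at least 50 randomised in permuted blocks stratified by centre.
- **That the sample size is wrong.** Both 50 and its confidence interval reproduce.
- **That the pilot's overall conclusion would generally be open to choice after the data are seen.** Only one value of one criterion is open in this way at N = 50.

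**Conclusion.** The point holds for the follow-up criterion alone. The label of 85% is wrong for 42 of 50: the count corresponds to 84%, and 85% requires 43. With 50 randomised, one result is affected, and its probability runs from 6.4% to 14.9% over true retention of 80 to 90%. The reading chosen moves the chance of meeting the criterion by 6.4 percentage points at 90% retention and by 14.9 at 85%. These figures assume exactly 50 randomised and independent completion with a common probability. The mismatch is small, but it lies in a pre-specified component of the primary outcome and should be corrected.

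**What to change.** In section 4.8, state one rule for the follow-up criterion before follow-up results are known. Either of these is coherent:

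- at least 85% of randomised participants with complete follow-up at two years (at least 43 of 50); or
- at least 84% of randomised participants (42 of 50), if 42 is the intended bar.

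In either case, add that the percentage governs if more than 50 are randomised. Leave the surgery-timing criterion and the sample size as they are.

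The cost is a one-line protocol correction, with no change to design or data collection. The one downside is that under the first option the bar may become one patient stricter than the count now printed.

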1.3. Recurrent Dislocations Have Devastating Impacts on Pain, Function and Quality of Life

By far, the most feared complication following a dislocation is a re-dislocation. Recurrent instability, experienced as a partial or complete dislocation of the humeral head from the glenoid socket post-initial dislocation, can reach upwards of 85%¹¹. Re-dislocation and continued instability results in decreased quality of life, shoulder pain, kinesiophobia and decreased physical activity and sport, as well as substantially increased costs over initial dislocation¹²⁻¹⁴. Recurrence mainly occurs in the first 2 years after the first anterior shoulder dislocation event, and 83% of patients who develop recurrent instability by 5 years do so within the first 2 years of a dislocation event¹¹. Surveys of patients demonstrate that 4 of 10 desire definitive treatment to limit further instability events and prefer surgery as their treatment of choice^{12,13}.

In addition to the health care costs of a dislocation, a prospective study of 257 patients followed for 25 years found that even if a patient does not sustain a subsequent complete re-dislocation, the presence of subtle instability can result in further labral tearing, cartilage injury, and glenoid and humeral bone erosion, which may increase the risk of developing arthritis. This is of critical concern to young active patients in whom this injury is most prevalent¹⁴.

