1.4. Rationales for Early Versus Delayed Surgical Intervention

Following the initial urgent management and relocation of a dislocated shoulder, the prevention of recurrent instability is the critical management consideration for health care providers and

surgeons. Two initial management options exist in patients with a FTD: non-operative care or surgical stabilization.

Non-Operative Care (Secondary Surgical Stabilization, if needed)

The current standard of care for the vast majority of FTDs is aggressive non-operative treatment with a brief period of immobilization (around 3 weeks) followed by a physiotherapy shoulder strengthening protocol¹⁵. Failure of non-operative management with a recurrent dislocation remains the indication for surgical stabilization or if there are further complaints of instability¹⁶. Proponents of this approach argue that approximately half of patients are adequately treated by non-operative methods alone without additional risks of surgery^{17,18}. Additionally, physicians and patients involved in seasonal sports often prefer non-operative treatment to allow a quick return to play and avoid ending the sporting season with a surgical procedure, despite the potential risk of increased instability. A cohort study by Shanley *et al.* found that 85% of athletes treated non-operatively following a shoulder dislocation returned to pre-injury sport for an entire season without a recurrent instability event¹⁹. Utilizing available risk stratification tools, those advocating for this approach believe that patients at high risk of recurrent instability – younger, involved in contact sports, or with subtle bony injury - are identified appropriately and the remainder can be treated non-operatively²⁰.

Primary Surgical Stabilization

Surgeons who prefer primary surgical stabilization of a FTD argue the following:

1. Evidence for early non-operative treatment is inconclusive;
2. Recurrent instability rates are unacceptably high;
3. Outcomes (shoulder stability and functional scores) following primary stabilization are superior to those of stabilization with recurrent instability;
4. Delay in treatment results in further injury to the joint, and;
5. Early surgical intervention more cost effective than initial non-operative management.

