4.2. Eligibility Criteria

Patients who meet the eligibility criteria outlined below are to be included in the study.

The inclusion criteria are:

1. Patients ages 14-40 years;
2. Diagnosis of first-time anterior shoulder dislocation having occurred within the past 3 months, confirmed either by radiographic evidence or documented reduction of anterior shoulder dislocation as well as physical examination eliciting unwanted glenohumeral translation with reproduction of symptoms;
3. Provision of informed consent.

The exclusion criteria are:

1. Patients that cannot undergo surgery or anesthesia;
2. Patients with concomitant injuries (rotator cuff tear, fracture);
3. Previous shoulder surgery;
4. Patients that will likely have problems with maintaining follow-up or are incarcerated;
5. Epilepsy/seizure disorder
6. Pregnancy;
7. Diagnosis of multidirectional instability;
8. Bony glenoid defect (bony Bankart) >10% as measured on preop imaging;
9. Dislocation without trauma, in a context of hyper laxity or atraumatic instability;
10. Cases involving litigation or workplace insurance claims (e.g. WSIB).

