4. Physical examination (range of motion and stability): Physical examination following surgery will be performed by the operating surgeon or an assigned delegate and will consist of functional assessment important to patients. Range of motion and shoulder stability are commonly reported outcome measures in the literature when assessing success following shoulder instability surgery^{30,31}. Range of motion will be assessed in forward flexion, abduction, ER and IR. Stability will be assessed primarily via the apprehension- relocation physical examination maneuver which has demonstrated the highest sensitivity in the literature for the diagnosis of anterior instability³². Presence of apprehension will be elicited by bringing the patient's shoulder into a position of 90° of abduction and 90° of external rotation in either the supine or upright position. A positive exam finding is the subjective feeling of impending subluxation or dislocation when in this provocative position. Relocation test is performed, positive test is resolution of feeling of impending subluxation.
5. Return to previous level of activity/sport and work: This outcome will be patient reported at each follow up visit. Time to return to sport will be based on when the patient is cleared by their treating surgeon to return. Time to return to work will reflect duration of work stoppage, if applicable. Specific dates of return to sport/work will be collected on study CRFs.
6. Safety: Rate of major and minor shoulder-related complications and serious adverse events.

Note: Feelings of recurrent instability or re-dislocation, regardless of group allocation and timing of onset, will be considered a treatment failure.

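### Crossover criterion 4 lets any reported feeling of recurrent instability, with no onset rule, exempt control-arm surgery, so early preference-driven operations can go uncounted

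*Protocol*

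**What the plan says.** Section 4.8 sets the fourth success criterion as "Less than 5 crossovers* between both groups". Its note defines two kinds of crossover:

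- **Control arm:** participants who "choose to undergo surgery in the absence of any feelings of recurrent instability or re-dislocation".
- **Surgery arm:** "participants randomized to surgical intervention who opt out of surgery prior to surgical intervention and choose to undergo primary non-operative management". No symptom exemption applies here.

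The note closing Section 4.9 adds: "Feelings of recurrent instability or re-dislocation, regardless of group allocation and timing of onset, will be considered a treatment failure". A control who has surgery and reports such a feeling is thus a treatment failure and not a crossover.

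Four other places bear on how easily the exemption is met:

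- Section 4.2 includes in the entry diagnosis a "physical examination eliciting unwanted glenohumeral translation with reproduction of symptoms".
- Section 4.9 says of the apprehension test: "A positive exam finding is the subjective feeling of impending subluxation or dislocation when in this provocative position".
- Section 4.4.1 states that neither the patient nor the treating surgeon can be blinded.
- Table 1 marks operative data and reoperation as applying to the intervention group only, and Section 4.10 likewise collects surgical details for that group only. Table 1 does schedule an assessment of crossovers and treatment failures at the surgery visit and at every follow-up visit.

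**The concern.** Criterion 4 is there to show whether patients can be kept on their allocated treatment. In this trial the obvious threat is a control patient who would rather have the operation. Section 3.0 says that the choice of treatment may depend heavily on preference, and Section 1.3 reports that 4 in 10 surveyed patients want definitive treatment and prefer surgery.

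Under the stated rule, whether such a patient is counted depends on a self-report with no severity threshold, no confirmation and no required onset. The patient giving it knows the allocation and wants the operation. If the feeling is reported, the operation leaves the crossover count, and none of the other three criteria (recruitment, follow-up, timely surgery in the surgical arm) would reveal it. The pilot could then support a definitive trial whose control arm does not hold.

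**Working it through.** **1. The plan's own figures.** The protocol gives no derivation for the limit of 5. As a share of the trial it is 5/50 = 10%. The sample size in Section 5.1 does reproduce: the Wilson 95% interval for 38/42 is 77.9% to 96.2% (stated as 78 to 96%), and 42/0.85 = 49.4, rounded up to 50. That calculation concerns precision around 90% compliance and does not settle what counts as a crossover.

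**2. Does the text require a new episode?** Section 4.8 names feelings and gives no onset rule. Section 4.9 sets timing of onset aside. Section 4.2 allows enrolment of patients whose symptoms were reproduced on examination. The grammar leaves open whether that examination goes with both diagnostic routes or only with documented reduction, but on either reading some patients may enter this way. Section 4.6 makes absence of apprehension a condition for discharge from physiotherapy, so the protocol expects that apprehension may persist during rehabilitation. Nothing in the operative definition prevents such a feeling from exempting an operation.

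**3. The count.** Criterion 4 compares with 5 the following sum:

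counted crossovers = (control operations with no reported feeling and no re-dislocation) + (surgery-arm opt-outs)

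Illustration: 8 of 25 controls are operated on early by preference, and surgery-arm opt-outs are 0.

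- All 8 report some feeling: 0 + 0 = 0, pass.
- All 8 counted: 8 + 0 = 8, fail (8/50 = 16% of the trial, 8/25 = 32% of controls).

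**4. Dependence on the self-report.** Let r be the proportion of controls operated on by preference with no new episode, and s the share of them who report no feeling at all. The counted number is Binomial(25, r × s). The table gives the probability of at most 4, with no surgery-arm opt-outs. The document supplies neither r nor s; both are assumptions.

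| r (expected operations) | s = 0 | s = 10% | s = 25% | s = 50% | s = 100% |
|---|---|---|---|---|---|
| 20% (5) | 100% | >99.9% | 99.3% | 90.2% | 42.1% |
| 30% (7.5) | 100% | 99.9% | 96.4% | 68.2% | 9.0% |
| 50% (12.5) | 100% | 99.3% | 80.5% | 21.4% | <0.1% |
| 100% (25) | 100% | 90.2% | 21.4% | <0.1% | 0% |

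The last column is what a rule counting every such operation would give. At r = 30%, the chance of passing runs from 9.0% to 100% according to what patients say about a feeling that the protocol does not define.

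**The case against.** The exemption is deliberate and, in principle, right. Section 1.4 describes later stabilisation as part of the non-operative strategy: "Failure of non-operative management with a recurrent dislocation remains the indication for surgical stabilization or if there are further complaints of instability". Surgery on that ground follows the assigned strategy and should not count as a crossover. This stands.

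The definition also speaks of recurrent instability, which Section 1.3 describes as "Recurrent instability, experienced as a partial or complete dislocation of the humeral head from the glenoid socket post-initial dislocation". On that reading, symptoms reproduced at entry belong to the first dislocation and do not qualify, and the words on timing in Section 4.9 may mean only early or late recurrence. This is a fair reading and may be what was meant. It is not what Section 4.8 fixes: the operative term there is feelings, the introductory description is not carried over, and no onset rule excludes entry symptoms. If a new episode is intended, one sentence would say so.

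Two further points have some force. Patients who refuse randomisation go to the non-randomised cohort, which should draw off the strongest preferences. Treatment failures are also assessed at every follow-up visit. But failure is defined by feelings or re-dislocation and not by surgery, so its count does not show how many controls were operated on.

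A reader might infer that criterion 4 passes however many controls have surgery. The documents do not support that. It would need nearly every operated control to report a feeling (with all 25 operated on and a quarter reporting none, the chance of passing is 21.4%), and five or more surgery-arm opt-outs fail the criterion in any case. Nor is there support for saying that it mainly counts surgery-arm opt-outs.

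**Conclusion.** The concern holds as a weakness in a stated counting rule for one of the four primary success criteria. Early preference-driven surgery in controls can be classed as treatment failure, and criterion 4 can then pass despite poor separation of the treatments. The possible size is the full number of such operations (8 counted as 0 in the illustration). The actual size is unknown, because the protocol gives neither the rate of such surgery nor the share of patients who would report a feeling.

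Three stronger inferences are not supported:

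- **A further 10 to 12 hidden control operations** (0.42 × 25 = 10.5; 0.47 × 25 = 11.75). This uses the highest reported recurrence rates as surgery rates. The protocol does not say that every recurrence leads to surgery, and such surgery is properly exempt.
- **An inflated failure rate carried into the definitive trial.** The Study Summary names recurrent dislocation and functional outcomes as that trial's targets, and Sections 2.2 and 4.9 list dislocations separately from instability symptoms. Relabelling an operation does not alter the dislocation count.
- **An error in counting surgery-arm events before surgery as failures.** This is a defensible choice when strategies are compared by allocation, as in the intention-to-treat analysis of Section 5.2.

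**What to change.** For counting purposes only, with no change to when surgery is offered:

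1. In Section 4.8, exempt a control operation from the crossover count only if a re-dislocation or instability episode with onset after randomisation was recorded before the decision to operate. Count other control surgery as crossover.
2. Beside criterion 4, report the total number of controls operated on by 24 months, by reason and timing.
3. Amend Table 1 and Section 4.10 so that the fact, date and reason of surgery are collected for the control arm too.
4. Confirm that the limit of fewer than 5 still suits the tighter definition, since the protocol gives no basis for it.

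The cost is a reworded definition, an onset date and a reason on the crossover and failure assessment already scheduled in Table 1, and one descriptive row in the report. The crossover count may look less favourable than under the present wording.
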